## 8.4 Enrollment Determination

Patients meeting all of the inclusion criteria and none of the exclusion criteria, can be considered for inclusion in the study.

# 9 Patient Enrollment

A minimum of 50 patients and a maximum of 75 patients.

The first 2 cases performed at each participating site will be evaluated to ensure compliance with the procedural guidelines and to determine the suitability of the imaging for review by the core lab. If it is determined that additional training on the procedural guidelines or revisions to the imaging parameters are required, then these patients will be excluded from the primary endpoint analysis.

## 9.1 Enrollment Phase

Patients are considered to be enrolled after signing the informed consent and having undergone a successful TCAR procedure (e.g. the procedure was not aborted due to technical issues or due to local complications the preclude stent implantation). Patients who are screened but do not meet all study criteria are considered screen failures and may not be enrolled.

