### 7.2 Secondary Endpoints

The following secondary endpoints will be assessed 0 to 30 days:

- All Stroke
- Neurological Death
- Volume of DW-MRI lesions
- Location of DW-MRI Lesions
- Stroke/Neurological Death in patients eligible for ROADSTER 2
- Stroke/Neurological Death in patients ineligible for ROADSTER 2
- Rate of contralateral new white lesions by DW-MRI

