## 9.2 Patient Numbering

Patients will be identified by a Patient Identification (ID) number, which is a combination of the specified site number and a sequential number assigned by the site. The Patient ID will consist of a 3-digit number and will be consecutively assigned.

Examples:

First Patient Enrolled at site #801: 801-001

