## 11.1 Follow-up

Study patient clinic evaluations must occur at multiple time-points post-procedure. The following tests or evaluations must be obtained:

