## **13 Adverse Events**

Adverse event (AE) data will be collected throughout the study and will be recorded on the Adverse Event CRF. For the purposes of this evaluation, adverse events include any stroke or neurological death.

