### **Acute Device Success**

Defined as ENROUTE Transcarotid NPS was delivered (vascular access achieved), reverse flow was attempted and established, and the device retrieved / removed from vasculature. If sheath placement is attempted but unsuccessful it will be considered an acute device failure. If procedure is aborted (e.g. patient isn't cooperative, change in health status, other extenuating circumstance, etc.) before both sheaths are placed or reverse flow is attempted it is not considered a device failure. Aborted procedures will not be included in Success rate calculations.

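### Enrolment requires a successful TCAR, so stroke and neurological death after an aborted attempt may be neither followed to day 30 nor counted

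*Protocol*

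**What the plan says.** Section 9.1 sets the condition for entry: "Patients are considered to be enrolled after signing the informed consent and having undergone a successful TCAR procedure". Its example of success is that "the procedure was not aborted due to technical issues or due to local complications" that rule out placing a stent. The same section reserves the label of screen failure for patients who do not meet the study criteria.

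Section 7.2 sets the clinical window: "The following secondary endpoints will be assessed 0 to 30 days". The list includes all stroke, neurological death, and the combination of the two by ROADSTER 2 eligibility. Day 0 includes the procedure.

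Other text bears on an aborted attempt only indirectly:

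- Section 13: "Adverse event (AE) data will be collected throughout the study", with adverse events defined as stroke or neurological death. Appendix 1 schedules adverse events from the procedure column onward.
- Section 11.1: "Study patient clinic evaluations must occur at multiple time-points post-procedure". Section 10.1 uses the term study patient at the consent stage, before any procedure.
- Section 9.2 illustrates the identifier with "First Patient Enrolled at site #801: 801-001".
- Section 9 states one analysis exclusion, for a site's first two cases where retraining or imaging changes are needed: "these patients will be excluded from the primary endpoint analysis". It does not concern the clinical endpoints.

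**The concern.** Entry to the study depends on how the treatment went, and it is decided after the risk period for stroke and death has begun. The reasons for non-entry that Section 9.1 names arise from the procedure; they are not baseline ineligibility. A stroke during or after an abandoned attempt could therefore leave both numerator and denominator.

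The estimates are the product here, since Section 14 plans no hypothesis test. A clinical rate limited to completed procedures answers a different question from a rate in all patients in whom TCAR was attempted, and a reader would need to know which is reported.

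A SAP can choose a denominator. It cannot recover 30-day examinations that sites did not perform because they took Section 9.1 at its word.

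**Working it through.** **Status of an eligible, consented patient whose attempt is aborted**

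1. Enrolled? No, by Section 9.1.
2. Screen failure? No, because the patient met the criteria.
3. Discontinued under Section 9.3? The listed factors are withdrawal, physician termination and loss to follow-up. The list is open-ended and does not mention aborted attempts.
4. Followed to day 30? Unclear. Section 11.1 applies to the study patient. Section 10.1 suggests this could include anyone who consented; Section 9.1 suggests it means enrolled patients.
5. Event recorded? An intraprocedural stroke plausibly is, under Section 13 and Appendix 1. A stroke on day 10 depends on the answer to step 4.
6. Event counted? Not stated. The enrolled group is the only overall patient set the protocol defines, so it is the inferred denominator.
7. Identifier assigned? Unclear, because the Section 9.2 example is tied to enrolment.

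A patient who is stented and then has a complication stays enrolled, so the gap is confined to aborted attempts.

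**Direction**

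With x events in N enrolled and e events in a aborted attempts:

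- enrolled rate = x/N
- attempted rate = (x + e)/(N + a)

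The attempted rate is the higher of the two exactly when e/a > x/N.

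**Illustration**

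The protocol states no figure to reproduce. N = 50 and 75 are its enrolment limits (Section 9). Exact intervals follow Section 14.1; the 95% level is assumed, since that section fixes none. The values of x, a and e are all assumed.

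| Enrolled | a | e | Attempted | 95% CI |
|---|---|---|---|---|
| 1/50 = 2.0% (0.05 to 10.6%) | 1 | 1 | 2/51 = 3.9% | 0.5 to 13.5% |
| | 3 | 1 | 2/53 = 3.8% | 0.5 to 13.0% |
| | 5 | 1 | 2/55 = 3.6% | 0.4 to 12.5% |
| | 5 | 0 | 1/55 = 1.8% | 0.05 to 9.7% |
| 1/75 = 1.3% (0.03 to 7.2%) | 1 | 1 | 2/76 = 2.6% | 0.3 to 9.2% |
| | 5 | 1 | 2/80 = 2.5% | 0.3 to 8.7% |
| | 5 | 0 | 1/80 = 1.25% | 0.03 to 6.8% |

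The rows with e = 1 assume event rates in aborted cases of 100% (a = 1), 33% (a = 3) and 20% (a = 5). They show what a single event does to the estimate; they do not forecast one.

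**A milder scenario**

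Take the two stroke/death rates cited in Section 3, 2.3% and 4.4%, as assumed base rates, with 50 completed and 5 aborted attempts.

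- Aborts at double the base rate: (50 × 2.3% + 5 × 4.6%)/55 = 2.5%, and (50 × 4.4% + 5 × 8.8%)/55 = 4.8%.
- Aborts at triple the base rate: (50 × 2.3% + 5 × 6.9%)/55 = 2.7%, and (50 × 4.4% + 5 × 13.2%)/55 = 5.2%.

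The expected shift is then 0.2 to 0.8 percentage points.

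**The case against.** The strongest reply is that Section 9.1 agrees with the stated design. Sections 1, 5 and 6 speak of patients treated with TCAR, or with the neuroprotection system together with the stent. A stroke rate in treated patients is a narrower quantity than a rate in attempted patients, but a legitimate one. This stands for the imaging endpoints, and it is a reason to keep a treated-set clinical rate. It does not settle whether aborted cases are followed, and the clinical endpoints in Section 7.2 carry no label limiting them to completed procedures.

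Analysis sets may also be defined in a SAP that is not shown. That is fair for the choice of denominator, but not for data collection.

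The consequence is limited: these are descriptive secondary endpoints, and Section 3 itself says that comparing stroke/death rates would take several thousand patients. That stands too.

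Three stronger readings are tempting, and the protocol does not support them:

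- **That the protocol discards failed attempts generally.** A reader might infer this from the Acute Device Success definition in Appendix 4: "Aborted procedures will not be included in Success rate calculations". The aborts described there occur before both sheaths are placed or reverse flow is attempted, and the same definition counts an unsuccessful sheath placement as a device failure. It concerns a success rate that is not a Section 7 endpoint and says nothing on follow-up for stroke or death.
- **That a successful TCAR means Procedure Success in Appendix 4,** which requires 30 days without death, stroke or myocardial infarction. Section 9.1 explains success by the absence of an abort and does not refer to that definition.
- **That the reported rates must be biased downward.** This holds only if aborted attempts have the higher event rate, and the protocol gives no data on that.

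**Conclusion.** The point holds in a limited form. Section 9.1 selects on a procedural outcome, the clinical window opens at day 0, and no text expressly requires that an aborted attempt be followed to day 30 or counted. Followed literally, the stroke and neurological death rates describe completed procedures. They are probably, not certainly, too low for attempted procedures.

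The size cannot be derived, because neither an abort rate nor an event rate in aborted cases is given. Under assumed counts, a single uncounted stroke roughly doubles the point estimate, while no stroke among the aborts lowers it slightly. In every case the exact intervals overlap widely, so what is at stake is the point estimate and the population it describes.

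The primary endpoint and the other DW-MRI endpoints are not affected: the objective concerns treated patients, and a completed, imaged set is acceptable if labelled. Severity is minor to should-fix, with moderate confidence, for secondary endpoints only. The main argument for acting is that uncollected data cannot be recovered later.

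**What to change.** Amend Sections 9.1 and 9.2 as follows:

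- Assign the identifier and record consented, eligible patients from a defined start of the TCAR attempt, for example the first access incision or puncture.
- Collect stroke and neurological death to day 30 in aborted cases.
- Report the number of aborted attempts, with reasons.
- Report the clinical rates for all attempted patients beside the treated-set rates, both labelled.
- Note any other carotid treatment received within the 30 days. Section 10.5 allows bailout and Appendix 4 defines emergent endarterectomy, so an event after an aborted attempt may follow another procedure.
- Keep the DW-MRI endpoints on the completed, imaged set, and say so.

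The cost is a short amendment and clinical follow-up of what should be a few extra patients, with no added imaging. The downsides are two denominators to label and possibly slightly less favourable clinical rates.

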## 9.2 Patient Numbering

Patients will be identified by a Patient Identification (ID) number, which is a combination of the specified site number and a sequential number assigned by the site. The Patient ID will consist of a 3-digit number and will be consecutively assigned.

Examples:

First Patient Enrolled at site #801: 801-001

## 9.3 Patient Discontinuation

If possible, every patient should remain in the study until completion of the required follow-up period; however, the patient's participation in the study may be discontinued at any time during the study. If this occurs, the reason for discontinuation should be documented in the source documentation, and Study Exit form must be completed. Factors leading to patient discontinuation may include, but are not limited to the following:

- **Patient Withdrawal:** Patient participation is voluntarily and the patient may discontinue participation (refuse all subsequent testing and follow-up) or withdraw their consent from the study at any time without affecting their future medical treatment or benefits.
- **Physician Termination:** The physician may terminate the patient's participation without regard to the patient's consent if the Physician believes it is medically necessary.
- **Lost to Follow-up:** A patient will be considered lost to follow-up only after three unsuccessful, documented attempts to contact the patient have been made.

## 10 Procedures

### 10.1 Informed Consent

Prior to patient participation in this evaluation, the Physician must obtain written Institutional Review Board approval for the protocol and the informed consent form. The approved consent form should clearly reflect the IRB/EC approval date and protocol version.

Once the patient's eligibility has been determined, the Physician or person designated by the Physician who has been trained to the protocol, will explain the nature and scope of the study, potential risks and benefits of participation, answer questions for the patient and ask the patient to participate in the study. The study will be explained to the study patient in lay terms and native language. If the patient agrees to participate, the informed consent must be signed and personally dated by the patient and the person completing the consent process. A copy of the signed and dated informed consent will be provided to the study patient. Study patients will be assured that they may withdraw from the study at any time and for any reason.

Failure to obtain a signed informed consent form prior to the procedure constitutes a major protocol deviation and non-compliance with internationally recognized good clinical practices per ISO 14155, the Declaration of Helsinki and the Code of Federal Regulations (21 CFR 50.20 General requirements for informed consent).

### 10.2 Diffusion-Weighted Magnetic Resonance Imaging (DW-MRI) Evaluation

A DW-MRI evaluation is to be done pre, post and 30 days post the index procedure. The following sequences should be used for each evaluation.

Magnetic resonance using a 3 Tesla MR imaging scanner. Sequences : T1, T2, T2\*, GRE, FLAIR, DWI and ADC map. Slice thickness: 4mm

**Table 1. DW-MRI visit windows**

Visit Window	Imaging Timing
Pre-procedure	≤ 72 hours prior to procedure
Post-procedure	Within 12 – 60 hours post procedure
30 days Post-procedure	30 days(-7/+15 days) post procedure

### 10.3 Pre-Procedure

Dual antiplatelet therapy and statin medications taken during the course of the study should be documented on the CRFs and a dosage indicated if possible.

**Table 2. Pre-procedure Testing and Evaluations**

Test / Evaluation	Timeframe Prior to Procedure (within # days)				
	180 days	60 days	30 days	7 days	≤ 72 hours
General Examination					
Medical History			✓		
Neurological Examination					
NIH Stroke Scale					✓
Modified Rankin Scale					✓
Imaging					
Bilateral Duplex Ultrasound (% of stenosis)			✓		
DW-MRI					✓
CTA of the head and neck	✓				

Every attempt should be made to have the same person conduct the exam at each visit.

#### 10.3.1 Pre-Procedure Medication Regimen

All medications should be administered per the following medication guidelines. All medications administered should be recorded on the patient's medical record and on the CRF throughout the duration of the trial. Prior to the procedure, all patients should receive the following medications:

**Table 3. Pre-Procedure Medication Regimen**

Medication	Dose	Time prior to procedure	Notes
Aspirin	75-325 mg*	At least 72 hrs	A 650 mg loading dose of aspirin, provided that it is not enteric coated or extended release, at least 4 hours prior to procedure is acceptable if 325 mg dosing was not administered prior to procedure or per the Institution's standard of care.
Clopidogrel	75 mg*	At least 72 hrs	A 450 mg clopidogrel loading dose at least 4 hours prior to procedure is acceptable if 75 mg dosing was not administered prior to procedure.  The physician may substitute Prasugrel, ticlopidine, ticagrelor or a generic version of Clopidogrel per the manufacturer's published guidelines.  If ticlopidine or ticagrelor is prescribed, it must be administered with the appropriate safety monitoring at two weeks and at one month.

Medication	Dose	Time prior to procedure	Notes
Statin	Therapeutic dose	Daily for at least 7 days	If possible, patients who are not currently on a statin should be started on a therapeutic dose for 7 days pre-procedure if not, use loading dose.  A loading dose at least 12 hours before procedure is acceptable if the patient is not already on a statin.

\*As stated in the "2011 ASA/ACCF/AHA/AANN/AANS/ACR/ASNR/CNS/SAIP/SCAI/SIR/SNIS/SVM/SVS guideline on the management of patients with extracranial carotid and vertebral artery disease: executive summary." and "ESVS Guidelines. Invasive Treatment for Carotid Stenosis: Indications, Techniques."

### 10.3.2 Pre-Procedure Contrast Preparation

Contrast should be drawn in to a manifold contrast injection system and allowed to rest undisturbed for a minimum of 20 minutes prior to planned usage.

At the discretion of the physician a syringe may be used for contrast injection. At least 20 minutes prior to use contrast should be drawn up into a least five 10ml luer lock syringes. Allow syringes to rest undisturbed for a minimum of 20 minutes prior to planned usage. Use of an automated contrast injector is recommended but not required.

## 10.4 TransCarotid Revascularization

### 10.4.1 Index Procedure

Responsibility for performing the index procedure may not be delegated to a Physician who has not been approved by the sponsor.

### 10.4.2 Procedural Medications

Heparin should be administered to achieve the desired activated clotting time (ACT). A sufficient dose should be given to achieve a target activated clotting time (ACT) of  $\geq 250$  seconds and maintained throughout the procedure.

At the discretion of the physician, procedural anticoagulation may be achieved with Angiomax (bivalirudin) which must be administered accordingly during the procedure.

The use of local or general anesthetic during the procedure is at the discretion of the physician.

**IMPORTANT: Pre-treatment with a thrombolytic agent or GP IIb/IIIa blocker is NOT allowed.**

### 10.4.3 Stenting TCAR Procedure

The ENROUTE Transcarotid Neuroprotection System (ENROUTE Transcarotid NPS) will be used for all index procedures in conjunction with the ENROUTE Transcarotid Stent System. Please refer to the IFU supplied with the ENROUTE Transcarotid NPS and Stent System for device preparation and placement.

Standard surgical means should be used to occlude the CCA during the index procedure.

After the ENROUTE Transcarotid NPS has been positioned, pre-dilatation of the lesion may be done prior to stent placement. Use an appropriately sized balloon to achieve a lumen diameter large

enough for passage of the stent delivery system. The appropriate size stent shall be selected after review of the patient's pre-procedure angiogram for determination of the reference vessel.

The choice of stent length should ensure complete coverage of the lesion. Only one stent should be used unless there is incomplete coverage of the target lesion or in the case of complications. For complications, an additional commercially available stent may be used.

**IMPORTANT:** Debulking devices, such as directional or rotational atherectomy and/or transluminal extraction coronary (TEC) devices may NOT be used.

## **10.5 Criteria for Bailout**

Bailout measures are at the discretion of the physician. Emergent endovascular therapy (neurovascular rescue) may be employed as necessary to provide the best medical care for the patient.

## **10.6 Mechanical Failures, Malfunctions or Device Defects**

All mechanical failures, malfunctions or defects involving any device component must be reported to the Sponsor in accordance with the FDA device reporting guidelines and EU Vigilance Reporting requirements.

## **10.7 Post-Index Procedure Medications**

All medications should be administered per the following medication guidelines. All medications administered should be recorded on the patient's medical record and on the CRF throughout the duration of the trial. After the procedure, all patients (lead-in and pivotal) should receive the following medications:

**Table 4.Post Procedure Medication Regimen**

Medication	Dose	Duration post-procedure
Aspirin	75 – 325 mg	Daily, continued indefinitely
Clopidogrel	75 mg	Daily, for minimum of 4 weeks
Statin	Therapeutic dose	Daily, for minimum of 4 weeks

## **11 Post Procedure Evaluation**

The following tests or procedures must be obtained as per schedule. These tests must be performed whether or not they are considered part of the Physician's standard of care.

**Table 5. Post-Procedure Testing and Evaluations**

Test / Evaluation	Timeframe Post-Procedure		
	Within 12 – 60 hrs post procedure	Within 24 hrs	Prior to Discharge
Neurological Examination			
NIH Stroke Scale		✓	
Modified Rankin Scale			
Imaging			
DW-MRI	✓		

Every attempt should be made to have the same person conduct the exam at each visit.

Prior to hospital discharge the study coordinator and/or Principal Physician at the site should ensure that the patient understands and complies with the required follow-up schedule. If possible, patients or family members may be given a calendar of required follow-up visits and telephoned by a member of the research team for a visit reminder, just prior to the follow-up date.

## 11.1 Follow-up

Study patient clinic evaluations must occur at multiple time-points post-procedure. The following tests or evaluations must be obtained:

**Table 6. 30-day Testing and Evaluations**

Test / Evaluation	30-days (-7/+15 days)
Neurological Examination	
NIH Stroke Scale	✓
Modified Rankin Scale	
Imaging	
Duplex Ultrasound (Bilateral)	✓
DW-MRI	✓

Every attempt should be made to have the same person conduct the exam at each visit.

## 12 Assessment of Safety and Performance

Performance and safety will be monitored continuously throughout the conduct of the study.

### 12.1 Clinical Follow-up Visits

Patients will be contacted for clinical follow-up office visit between 30 and 45 days post procedure.

Appendix 1. Schedule of Events outlines the evaluations that are be done at each time point.

### 12.2 Additional Follow-up Visits

Additional patient visits may occur as clinically warranted.

## **13 Adverse Events**

Adverse event (AE) data will be collected throughout the study and will be recorded on the Adverse Event CRF. For the purposes of this evaluation, adverse events include any stroke or neurological death.

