### **Cranial Nerve Palsy or Injury**

Injury to cranial nerves in the vicinity of the treated carotid artery that has not resolved by one month and six months after the initial procedure. Symptoms will depend on the specific nerve that is injured, such as difficulty swallowing or paralysis of facial muscles.

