#### **Device Related Adverse Event**

An undesirable event that was directly caused by the device.

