### Major Adverse Event (MAE) Rate

A composite rate of death, stroke and myocardial infarction

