### Procedure Related Adverse Event

An undesirable event that occurred as a direct cause of the procedure that was not a direct cause of the device.

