### Procedure Success

Technical Success without the occurrence of MAE 30-days post procedure.

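### Section 13 names only stroke and neurological death as adverse events, which is narrower than MAE, Procedure Success and the summary's Stroke/Death endpoint require

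*Protocol*

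**What the plan says.** Section 13 sets both the record and its scope. On the record: "Adverse event (AE) data will be collected throughout the study and will be recorded on the Adverse Event CRF". On the scope: "For the purposes of this evaluation, adverse events include any stroke or neurological death".

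Appendix 4 defines several measures on a wider set of events:
- MAE is "A composite rate of death, stroke and myocardial infarction", with death not restricted by cause.
- Procedure Success is "Technical Success without the occurrence of MAE 30-days post procedure".
- A device-related adverse event is "An undesirable event that was directly caused by the device", and a procedure-related one is "An undesirable event that occurred as a direct cause of the procedure that was not a direct cause of the device".
- Cranial nerve injury is a deficit that "has not resolved by one month and six months after the initial procedure".

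Appendix 4 also separates neurologic, cardiac and other death.

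The two endpoint lists differ on death. Section 1 has Stroke/Death in patients eligible and ineligible for ROADSTER 2. Section 7.2 restricts the same two composites to neurological death.

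Section 12 adds a general commitment: "Performance and safety will be monitored continuously throughout the conduct of the study".

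**The concern.** A myocardial infarction or a cardiac death within 30 days is not among the events that Section 13 names, yet either one is an MAE and ends Procedure Success. A cardiac death also counts towards Stroke/Death as Section 1 words it. If the Adverse Event form is filled in as Section 13 reads, these events need not appear on it.

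Two things are at stake. First, a rate of MAE, Procedure Success or Stroke/Death taken from that form would be incomplete, and always in the flattering direction. Second, the site decides whether a death was neurological before it is recorded as an adverse event, so a misattributed death leaves no adverse event entry to check. That sits poorly with the monitoring commitment in Section 12, and with Section 4.1, which allows later iterations of the neuroprotection system during the study.

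**Working it through.** The protocol gives no event rate, power or precision figure on this point, so there is nothing to reproduce. The check sets the sections side by side.

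**Events needed against events named**

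| Measure | Needs | Named in Section 13 | Not named |
|---|---|---|---|
| Section 7.2 clinical endpoints | stroke, neurological death | both | none |
| Stroke/Death (Section 1) | stroke, any death | stroke, neurological death | cardiac and other death |
| MAE (Appendix 4) | stroke, any death, myocardial infarction | stroke, neurological death | cardiac and other death, myocardial infarction |
| Procedure Success (Appendix 4) | Technical Success and no MAE at 30 days | as for MAE | as for MAE |
| Device- or procedure-related event (Appendix 4) | any undesirable event so caused | only strokes and neurological deaths | all others |

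The Appendix 4 SAE definition does not widen the scope. It selects from adverse events, so read with Section 13 it covers only some strokes and neurological deaths.

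**Direction.** An unrecorded event can remove a patient from the MAE or Stroke/Death numerator but cannot add one. MAE and Stroke/Death could therefore only be too low, and Procedure Success only too high. A patient who also had a recorded stroke is already counted, so the error arises only in patients whose sole qualifying event is unnamed.

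**Size.** Let q be the combined 30-day rate of myocardial infarction and non-neurological death. The documents do not give q, so the values below are assumptions. Section 9 gives n = 50 to 75. The expected number is nq, and the chance of at least one is 1 − (1 − q)^n. For example, with q = 1% and n = 75, 1 − 0.99^75 = 1 − 0.471 = 0.529.

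| Assumed q | n = 50: expected, chance of at least one | n = 75: expected, chance of at least one |
|---|---|---|
| 0.5% | 0.25, 22% | 0.375, 31% |
| 1% | 0.5, 39% | 0.75, 53% |
| 2% | 1.0, 64% | 1.5, 78% |
| 4% | 2.0, 87% | 3.0, 95% |

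These are chances that an unnamed event occurs, not estimates of bias. How many would go unrecorded depends on forms that are not shown.

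**Cranial nerve injury.** The only follow-up visit is at 30 days, −7/+15, so it falls between day 30 − 7 = 23 and day 30 + 15 = 45. The definition also needs status at six months, about day 180. No scheduled contact reaches that point, so the definition cannot be assessed in any patient.

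**The case against.** The strongest reply is that nothing planned depends on these definitions. MAE, Procedure Success, device- and procedure-related events and cranial nerve injury are in neither endpoint list, and Section 14 plans no analysis of them. Section 13 matches the Section 7.2 clinical endpoints exactly, which is a defensible choice for a study that Section 22 calls a non-interventional post-market evaluation. Appendix 4 also looks carried over from another protocol: its access-site entry cites a Section 12.1 on wound management, whereas Section 12.1 here covers clinical follow-up visits. All of this stands, and it limits the point.

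It does not dispose of it. Section 1 still lists Stroke/Death, Section 12 still promises safety monitoring, and the cause-of-death filter remains.

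A second reply is that Section 13 says adverse events include the two named events, not that they are limited to them. The Procedure, Devices, Follow-up and Study Exit forms are held separately, a Study Exit form is required on discontinuation (Section 9.3), and device malfunctions are reported under Section 10.6. This also stands in part: a death or infarction might be noted somewhere. But if the scope is open, the protocol does not say what else to record as an adverse event, and sites may differ. Section 15.2 hints at a wider scope by listing ECGs and catheterization reports as supporting documents for adverse events.

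A reader might infer more than the text supports:
- That the study's safety results will look better than they are. This assumes that MAE or Procedure Success will be reported, which the protocol does not say. Any SAP was not available to check.
- That the unnamed events are not captured anywhere. The forms cannot be inspected, and stroke and neurological death, which are part of MAE, are collected.
- That a local wound or stent complication would be misclassified as Procedure Success. Without death, stroke or myocardial infarction it is not an MAE, so a patient with Technical Success is a Procedure Success by definition even with complete recording.
- That the weight of one patient, 1/75 to 1/50, measures the bias. It is only the weight of one event.

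**Conclusion.** The mismatch is real and limited. Section 13 does not name myocardial infarction or non-neurological death, and no other section requires either to be recorded as an adverse event. MAE and Procedure Success need both, and Stroke/Death in Section 1 needs all deaths. If any of these is reported from the Adverse Event form alone, the error can run only in favour of the procedure. Its size cannot be derived from the documents. Under the assumed rates, at least one relevant event is anything from unlikely (22%) to near certain (95%).

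The DW-MRI primary endpoint and all Section 7.2 endpoints are unaffected. The six-month cranial nerve criterion cannot be assessed, which yields no result rather than a favourable one. This is a worthwhile low-cost improvement, not a threat to the main result.

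**What to change.** In Section 13, define adverse events as any death (with cause classified by the Appendix 4 categories), stroke, myocardial infarction, and any device- or procedure-related event that meets the Appendix 4 SAE criteria. Collect them from the start of the procedure to the 30-day visit, on the existing Adverse Event form. Recording every death and classifying its cause afterwards removes the filter at the point of entry.

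Align the death component of the Section 1 composites with Section 7.2. Either assess cranial nerve injury at the 30-day visit and reword its definition to match, or delete it. Delete the other Appendix 4 definitions that the study will not use.

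The cost is a wording amendment, added categories on one form and a modest amount of data entry. Appendix 1 already schedules adverse event contacts at the procedure, within 24 hours, before discharge and at the 30-day visit, so no new visit is needed. Deleting the unused definitions alone would tidy the text but leave the recording of deaths and infarctions unchanged.
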